4.9.2 Primary Efficacy Variable – UACR

The primary estimand is a hypothetical estimand such that the treatment effect is quantified in the optimal situation where any potential confounder is avoided. The population of interest is the per protocol population. The endpoint being assessed is the change in log-transformed urine ACR from baseline to Week 20. For the intercurrent event, if a participant discontinues treatment due to AE or lack of efficacy, or uses prohibited medication, the urine ACR data are treated as missing after the event and no imputation is performed. The summary measure being evaluated is the geometric mean reduction of urine ACR from baseline to Week 20.

4.9.2.1 Primary Analysis

The primary efficacy endpoint for this study is the reduction of urine ACR from baseline to Week 20 compared to placebo (on treatment with dapagliflozin as future standard of care). As urine ACR is assumed to follow a log-normal distribution, it will be log-transformed for statistical analysis purposes. The mean log changes in urine ACR at Week 20 ($\hat{Y}_1, \hat{Y}_2, \hat{Y}_3, \hat{Y}_4$) for each of the 3 AZD5718 doses and placebo will be estimated in a mixed model for repeated measures [MMRM] (Weeks 2, 4, 8, 12, 16, and 20). The values will be back transformed onto the original scale to give the geometric mean relative change from baseline at Week 20. The analysis model will include the fixed categorical effects of stratification factor, treatment, visit, and treatment-by-visit interaction, plus the continuous covariates of baseline log (urine ACR) and baseline log (urine ACR)-by-visit interaction. An unstructured covariance structure will be used for the within-participant errors. A homogeneity assessment between the DM and the non-DM sub-populations will be performed. Denominator degrees of freedom will be estimated using the Kenward-Roger approximation. If the MMRM model does not converge using an unstructured covariance structure, the heterogeneous Toeplitz covariance structure will be evaluated, followed by the heterogeneous autoregressive of first order, heterogeneous compound symmetry, and homogeneous compound symmetry covariance structures in the case of further non-convergence. If none of the models converge, the analysis will be altered to use an analysis of covariance (ANCOVA) with last observation carried forward (LOCF) imputation method implemented.

The point estimates from the model, including the 95% CIs and p-values will be presented. The point estimate and 95% CI for the geometric mean ratio will be converted to the percentage change as follows:

$$[(\text{Geometric Mean Ratio} - 1) \times 100]$$

The UACR will be summarized by treatment group and visit in terms of absolute values and changes from baseline.

The primary analysis will be repeated by strata (DKD without SGLT2i background, DKD with SGLT2i background, non-DKD), with the analysis model will include the fixed categorical effects of treatment, visit, and treatment-by-visit interaction, plus the continuous covariates of baseline log (urine ACR) and baseline log (urine ACR)-by-visit interaction.

A plot showing the mean percentage change from baseline in UACR over time within each treatment group will be provided.

A by-participant listing of the UACR data will be provided.

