Abbreviations: 5-LO = 5-lipoxygenase; ACR = albumin to creatinine ratio; AEs = adverse events; CCI [REDACTED]; CKD = chronic kidney disease; CSR = clinical study report; CCI [REDACTED]; DKD = diabetic kidney disease; CCI [REDACTED]; ECG = electrocardiograms; eGFR = estimated glomerular filtration rate; CCI [REDACTED]; CCI [REDACTED]; CCI [REDACTED]; CCI [REDACTED]; PK = pharmacokinetics; CCI [REDACTED];

SAEs = serious adverse events; SBP = systolic blood pressure

^a Will be reported outside of the CSR

Overall Design

This is a Phase 2b, randomised, double-blind, placebo-controlled, multi-centre, dose-ranging study to evaluate the efficacy, safety and PK of AZD5718 in participants with proteinuric CKD.

The study will be conducted in approximately 118 study centres across 12 countries.

Approximately 632 participants comprising of 67% DKD and 33% non-DKD participants will

be randomised 1:1:1:1 to receive once daily oral doses of [redacted] mg AZD5718, [redacted] mg AZD5718, [redacted] mg AZD5718, or placebo, for the first 12 weeks with an add-on therapy of 8 weeks of dapagliflozin for all participants, to have 158 participants per group. The plan is to have approximately 568 evaluable participants (142 per group) completing the study.

Disclosure Statement: This is a double-blinded placebo-controlled treatment study with 4 arms.

Number of Participants:

Approximately 632 participants will be enrolled to achieve 568 evaluable participants (142 per group).

Intervention Groups and Duration:

The study will include 4 intervention groups: [redacted] mg AZD5718, [redacted] mg AZD5718, [redacted] mg AZD5718, and placebo for the first 12 weeks followed by the addition of dapagliflozin to all participants from Week 12 to 20.

The study will include 4 periods:

- Screening Period of up to 4 weeks
- Treatment Period 1 consisting of 12 weeks where the participants will receive a once daily oral dose of the assigned dose of study drug to be taken with approximately 200 mL water in the morning with no restrictions on food intake.

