4.9.1.4 Handling of Dropouts or Missing Data

Summary statistics will be based on non-missing values. For analyses of UACR, if a measurement is missing it will not be imputed. Missing safety data will generally not be imputed. However, safety assessment values (vital signs, laboratory assessments excluding urine albumin, urine creatinine and UACR) of the form of “< x” (ie, below the lower limit of quantification) or > x (ie, above the upper limit of quantification) will be imputed as “x” in the calculation of summary statistics but displayed as “< x” or “> x” in the listings. Measurements of urine creatinine, urine albumin and UACR which are displayed as “< x” or “> x” will be imputed by Covance Central Laboratory in order to effectively calculate the geometric mean.

Partial or missing dates

If the start date of the concomitant medication, medical history relating to T2DM diagnosis or AE is missing, the following rules will be applied:

- If the year is missing, the year should be imputed as the year that participant received the first dose of study treatment.
- If the year is available and the month and day are missing, then impute the month as January and the day as 01.
- If the year and month are available and the day is missing, impute the day as 01 (the first day of the month).
- If any of the above puts the date before the date of first dose of study treatment, a conservative approach is followed and, the date is imputed using the date of first dose.

If the stop date of the concomitant medication or AE is missing, the following rules will be applied:

- If the year is missing, the year should be imputed as the year that participant received the last dose of study treatment.
- If the year is available and the month and day are missing, then impute the month as December and the day as 31.
- If the year and month are available and the day is missing, impute the day as the last day of the month (eg, 28, 29, 30, or 31).
- It is not expected to have missing dates for unscheduled laboratory or ECG data. However, if there are missing dates, for any derivations, the dates should be imputed following the rules for concomitant medications and AEs.

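### SAP 4.9.2.1's last-resort ANCOVA with LOCF contradicts the SAP's no-imputation rule for UACR and could count a pre-dapagliflozin value as Week 20

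*SAP*

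**What the plan says.** SAP 4.9.2.1 fits an MMRM to log UACR at "Weeks 2, 4, 8, 12, 16, and 20" with an unstructured covariance matrix. If that fails, it tries heterogeneous Toeplitz, then heterogeneous first-order autoregressive, then "heterogeneous compound symmetry, and homogeneous compound symmetry covariance structures in the case of further non-convergence". If all five fail, "the analysis will be altered to use an analysis of covariance (ANCOVA) with last observation carried forward (LOCF) imputation method implemented".

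Two other places in the SAP give the missing-data rule for the same variable. Section 4.9.1.4 states: "For analyses of UACR, if a measurement is missing it will not be imputed". The primary estimand in 4.9.2 covers stopping treatment for an adverse event or lack of efficacy, and use of prohibited medication. In those cases "the urine ACR data are treated as missing after the event and no imputation is performed". The protocol gives the same estimand in Sections 3 and 9.4.2.1. None of these sections makes an exception for the fallback.

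The Week 20 endpoint is defined as on dapagliflozin. The Protocol Synopsis describes the four arms for 12 weeks, "followed by the addition of dapagliflozin to all participants from Week 12 to 20".

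**The concern.** A fallback should estimate the same quantity as the model it replaces, under the same missing-data rule. This one does neither.

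- It imputes where the SAP says that UACR is not imputed. That includes values which the estimand has just removed after an intercurrent event.
- Background treatment changes for every arm between Week 12 and Week 20. LOCF ignores that change. A value carried from Week 12 or earlier would be analysed as a Week 20 value on dapagliflozin, although it was taken before the first study dose of dapagliflozin.

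At stake are each arm's geometric mean reduction at Week 20 and, under conditions set out below, the placebo-adjusted contrast.

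**Working it through.** No planned figure needs reproducing. The power, effect, SD and discontinuation rate behind the sample size are redacted, and the point does not depend on them.

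**1. Can a pre-dapagliflozin value reach Week 20?** Yes, under the written rules.

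- UACR is collected before study drug on a visit day (Protocol Table 1, footnote h). The Week 12 sample therefore precedes the first study dapagliflozin dose, and only Weeks 16 and 20 are on it.
- Per Protocol membership requires receipt of dapagliflozin after Week 12. It does not require a Week 16 or Week 20 UACR (SAP Table 3).
- The Discontinuation Visit is left out of the mapping to analysis visits (SAP 4.2). An on-dapagliflozin sample taken there may not replace the Week 12 value.
- A participant who stops for an adverse event before Visit 8 is expected to keep attending (Protocol 7.1). The estimand removes the later values, and LOCF would then insert Week 12.

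A participant with a usable Week 16 value but no Week 20 value carries an on-dapagliflozin value, so this mismatch does not arise for that participant.

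**2. How large could the effect be?** Inputs that the documents do not give, and which are assumed here:

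- D, the proportional UACR reduction from dapagliflozin: 20% to 35%.
- pA and pP, the shares of the AZD5718 and placebo arms whose Week 12 value stands in for Week 20, with missingness unrelated to outcome.

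The true placebo-adjusted reduction is set at 30%, the target value in SAP Appendix B.

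*Within an arm.* The Week 20 geometric mean is multiplied by (1 − D)^(−p). With p = 10% this is 0.80^(−0.1) = 1.023 to 0.65^(−0.1) = 1.044. With p = 20% it is 1.046 to 1.090.

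*Contrast, AZD5718 effect equal at Weeks 12 and 20.* The log ratio becomes ln(0.70) − (pA − pP) × ln(1 − D).

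- Equal shares: the second term is zero and there is no bias.
- pA − pP = +0.10, D = 20%: 1 − 0.70 × exp(0.1 × 0.223) = 28.4%.
- pA − pP = +0.10, D = 35%: 1 − 0.70 × exp(0.1 × 0.431) = 26.9%.
- pA − pP = −0.10: 31.5% (D = 20%) and 33.0% (D = 35%).

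A simulation with 400,000 per arm agrees with the formula. It assumed D = 25%, SD 0.8 and correlation 0.6. Equal shares of 10% and 20% gave 30.3% and 30.1%. Shares of 20% on AZD5718 and 10% on placebo gave 28.1% (formula 28.0%), and the reverse gave 32.1% (formula 32.0%).

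*Contrast, equal shares p but different AZD5718 effects at the two visits.* The log ratio becomes (1 − p) × ln(R20) + p × ln(R12), where R20 and R12 are the true placebo-adjusted ratios. Suppose the reductions are 30% at Week 12 and 20% at Week 20.

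- p = 10%: 1 − exp(0.9 × ln 0.80 + 0.1 × ln 0.70) = 21.1%.
- p = 30%: 1 − exp(0.7 × ln 0.80 + 0.3 × ln 0.70) = 23.1%.

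The true Week 20 value is 20%, so equal missingness alone does not guarantee an unbiased contrast.

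**3. Where else does the fallback apply?** SAP 4.9.3.1 uses the same methods for Week 12, and Appendix B uses the MMRM of 4.9.2.1 at the interim. At Week 12 every carried value would also precede study dapagliflozin, so only the conflict with the no-imputation rule remains there.

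**The case against.** The strongest reply is that the step will almost never run. Five structures must fail, and the last, homogeneous compound symmetry, has two covariance parameters. That stands, and it is why the point is minor.

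A reader might infer that the by-strata repeats would reach LOCF, by applying the quoted SGLT2i uptake of under 5% to the DKD participants and finding a tiny stratum. The documents do not support this. That uptake describes patients in general, not enrolment in this trial, which gives DKD with SGLT2i background its own randomisation strata. A large number of treatment-by-visit means relative to participants also concerns the fixed effects, not covariance convergence. Participants already on an SGLT2i switch to dapagliflozin at Week 12 (Protocol 6.5.2), so the assumed 20–35% step need not apply to them.

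A reader might also take the 273 of 613 who did not complete treatment (613 − 340; 44.5%) as the carried share. That count covers all randomised participants. It can include people who never started dapagliflozin and so are outside the Per Protocol set, and people with a Week 16 value. It also follows the sponsor's termination of the study. Nothing in the documents indicates that the loss differed by arm.

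Finally, the assumed 10-point difference is large. It concerns loss between Visits 7 and 8 only, yet it matches the whole planned allowance (1 − 142/158 = 10.1%). This objection stands: the figures show the mechanism and do not predict the bias.

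**Conclusion.** The contradiction holds as written: SAP 4.9.2.1 ends in an imputation that 4.9.1.4 and 4.9.2 exclude. If the step were used, some Per Protocol participants could have a pre-study-dapagliflozin value analysed as the on-dapagliflozin endpoint. Severity is minor, because the step is unlikely to be reached.

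The illustrated size, 26.9–28.4% or 31.5–33.0% in place of 30%, rests on the assumed dapagliflozin effect and the assumed difference in carried shares. With equal shares and a constant AZD5718 effect the contrast is unbiased, and only the within-arm reductions are understated. A reader might infer that LOCF works against AZD5718. The documents do not support a fixed direction: it depends on which arm has more carried values and on whether the AZD5718 effect changes after Week 12. Nor do they show that any planned result will rest on this step.

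**What to change.** Replace the LOCF sentence in SAP 4.9.2.1. Suggested content: if none of the covariance structures converges, change from baseline in log UACR at Week 20 will be analysed by ANCOVA on observed Week 20 values. The estimand's rule for intercurrent events is applied first, the same baseline covariates are used, and nothing is imputed. For the Week 12 analysis in 4.9.3.1, use observed Week 12 values in the same way.

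The cost is one sentence. It needs no new data and does not change the main fit. If this fallback is reached, it drops participants without a Week 20 value, makes no use of their earlier visits and loses some precision. Multiple imputation would use those visits, but it breaches the same no-imputation wording unless 4.9.1.4 is given an explicit exception. Writing an exception for LOCF would remove the textual conflict but not the mismatch in background treatment.

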4.9 Efficacy Evaluation

4.9.1 Analysis and Data Conventions

This study is designed to test for superiority and assess the dose-response relationship. The null hypothesis for the treatment comparison will be that there is no difference between AZD5718 with dapagliflozin and placebo with dapagliflozin on urine ACR. The alternative hypothesis will be that there is a difference. Symbolically, this is expressed as follows:

$$H(0): \mu(\text{AZD5718+dapagliflozin}) = \mu(\text{placebo} + \text{dapagliflozin})$$

$$H(1): \mu(\text{AZD5718+dapagliflozin}) \neq \mu(\text{placebo} + \text{dapagliflozin})$$

A 2-sided test with $\alpha = 0.1$ will be used to test this hypothesis.

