4.9.1.6 Examination of Sub-groups

Sub-group analyses for the primary efficacy endpoint by SGLT2i background and by DKD status will be presented. Summaries of the primary efficacy variable by treatment group and sub-group will also be produced. No formal statistical analysis will be performed within these sub-group.

A forest plot will present the least-squares mean and 90% CI overall and for each sub-group individually. These will be taken from the primary analysis model.

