4.9.3 Secondary Efficacy Variables

4.9.3.1 UACR at 12 Weeks

Urine ACR will be analysed to determine the dose-response effect of AZD5718 at 12 weeks (on current standard of care). The population of interest are randomised participants who meet all eligibility criteria and have valid non-missing urine ACR records at baseline and at least one post-treatment visit. The mean log change from baseline in urine ACR will be analysed using a mixed model for repeated measures. The summary measure being evaluated is the geometric mean reduction of urine ACR from baseline to Week 12. This will be evaluated using the same methods for the primary efficacy endpoint. The analysis will be repeated on the Per-Protocol Analysis Population.

The results of the model parameters (estimates, p-values, and 95% CIs) will be presented. The point estimate and 95% CI for the geometric mean ratio will be converted to the percentage change as follows:

$$[(\text{Geometric Mean Ratio} - 1) \times 100]$$

UACR will be summarized by treatment group and visit in terms of absolute values and changes from baseline.

The analysis will be repeated by strata (DKD without SGLT2i background, DKD with SGLT2i background, non-DKD), with the analysis model will include the fixed categorical effects of treatment, visit, and treatment-by-visit interaction, plus the continuous covariates of baseline log (urine ACR) and baseline log (urine ACR)-by-visit interaction.

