1. There should be at least 50% of successful measurements in both day-time (06:01 to 22:00) and night-time (22:01 to 06:00). If both the scheduled and repeat assessment sessions have more than 50% of successful measurements in the respective timeframes, the assessment session with a higher overall percentage of successful measurements will be included in the analyses. In the unlikely event that both the scheduled and repeated assessment sessions have the same percentage of successful measurements (and both above 50%), the scheduled assessment session will be taken as the visit assessment.
2. There are not more than two consecutive hours with no available measurements in an ABPM assessment session.

Primary ABPM Analysis

The primary endpoint in the analysis is the change from baseline in 24-hour mean SBP at Week 12. Participants with missing mean 24-hour SBP at Week 12 will be excluded from the analysis.

In order to derive the mean SBP over various time periods, the hourly mean SBP is derived for each participant for each hour using the available data at the visit. This is the sum of the successful non-missing SBP measurements in the hour, divided by the number of non-missing SBP measurements in the respective hour. This derivation will be used to further derive the endpoints of interest.

The 24-hour mean SBP is derived as the sum of the non-missing hourly mean SBP measurements, divided by the number of hours with non-missing hourly mean SBP. Missing hourly mean SBP derivations will not be counted towards the 24-hour mean.

For the ABPM analysis, baseline for the 24-hour mean ABPM parameter (or mean day-time, mean night-time, mean hourly) is defined as the 24-hour mean value (or corresponding mean day-time value, mean night-time value, mean hourly value) during the Screening Visit 2.

The change from baseline in 24-hour mean SBP at Week 12 will be analysed using an ANCOVA model, with change from baseline in 24-hour mean SBP as the dependent variable, adjusting for DM stratification factor, treatment group (AZD5718 **CC** mg, AZD5718 **CC** mg, AZD5718 **CC** mg, placebo), plus baseline 24-hour mean SBP and BMI as covariates. The ambulatory blood pressure monitoring population will be used for this analysis. The least squares (LS) mean difference between each of the AZD5718 doses and placebo (ie, placebo-corrected change from baseline in 24-hour mean SBP) will be derived from the model. The 2-sided 90% CI for these differences will be presented.

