If the proportion of participants within a sub-group category is too small for effective analyses, sub-group categories can be collapsed or removed from the sub-group analyses, where appropriate.

The change from baseline in 24-hour mean DBP at Week 12 will be analysed similarly to the primary endpoint using an ANCOVA model. The 2-sided 90% CI for the difference between each of the AZD5718 doses and placebo will be derived from the model and presented.

Sensitivity ABPM Analysis – 24-hour Mean SBP

The proportion of missingness of ABPM data (the number of participants who did not meet either of the statistical validity criteria at baseline and Week 12) will be summarised by treatment group and by key baseline characteristics (age group, race, BMI group, and randomisation strata).

Secondary ABPM Analysis

The secondary ABPM endpoints are change from baseline in mean day-time and mean night-time ABPM metrics (SBP and DBP), these will be evaluated similarly to the primary ABPM endpoint using ANCOVA models, presenting only the 90% CI between each of the AZD5718 doses and placebo. No formal hypothesis testing will be performed. Day-time is defined as 09:00 to 21:00, night-time is defined as 01:00 to 06:00.

The mean day-time SBP will be derived as the sum of the hourly mean SBP from 09:00 to 21:00 divided by the total number of hours with non-missing data. The mean night-time SBP will be derived as the sum of the hourly mean SBP from 01:00 to 06:00 divided by the total number of hours with non-missing data. The same derivations will be performed for DBP. Summary statistics will be presented for mean day-time and night-time values.

By-participant listing for ambulatory blood pressure monitoring values and derivations will be presented by treatment group and visit.

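### The Week 20 UACR comparison is tested at two-sided 0.10 but reported with 95% intervals, and the sub-group forest plot, as sourced, forces equal treatment effects in every sub-group

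*SAP*

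**What the plan says.** **Test level.** SAP 4.9.1 states the null and alternative for AZD5718 with dapagliflozin against placebo with dapagliflozin on urine ACR. It says that a two-sided test with alpha 0.1 "will be used to test this hypothesis".

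**Interval level.** For the Week 20 analysis, SAP 4.9.2.1 says "The point estimates from the model, including the 95% CIs and p-values will be presented". SAP 4.9.1.6, on the same endpoint, says "A forest plot will present the least-squares mean and 90% CI overall and for each sub-group individually".

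**Forest-plot source.** SAP 4.9.1.6 opens with "Sub-group analyses for the primary efficacy endpoint by SGLT2i background and by DKD status will be presented". After describing the plot it adds "These will be taken from the primary analysis model". It also says that no formal analysis is done within sub-groups.

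**The primary model.** SAP 4.9.1.3 and 4.9.2.1 together give DKD status and SGLT2i history as stratification variables, plus treatment, visit, baseline log UACR, treatment-by-visit and baseline-by-visit. No term crosses treatment with a stratification variable. SAP 4.9.2.1 also plans refits in three strata (DKD without SGLT2i background, DKD with it, and non-DKD) and a DM versus non-DM homogeneity assessment with no method given.

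**The concern.** A test at two-sided 0.10 corresponds to a 90% interval, and a 95% interval corresponds to a test at 0.05. The report would judge the primary comparison at one level and display its uncertainty at another, while the forest plot of the same endpoint uses the first level. No sentence calls the 95% interval descriptive. A reader who judges by the interval and one who judges by the p-value can reach different conclusions about the same dose.

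A sub-group forest plot exists to show whether the effect differs between sub-groups. If its rows come from a model in which the effect is not allowed to differ, equal rows say nothing about the data. A reader would take them as evidence of consistency.

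**Working it through.** **1. Interval against test**

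Inputs: alpha 0.10 two-sided (SAP 4.9.1); 95% CI (SAP 4.9.2.1); 142 evaluable per group (SAP 4.13). Power, effect and SD are redacted in SAP 4.13, so the sample-size calculation cannot be reproduced and ranges are assumed.

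- Width: 1.645 / 1.960 = 0.839. On the log scale the 90% interval is 16% narrower than the 95% interval.
- No true effect: P(0.05 < p < 0.10) = 0.10 − 0.05 = 5% per comparison, half of it (2.5%) in the favourable direction.
- Planned effect, with power at alpha 0.10 assumed: the standardised effect is d = 1.645 + z(power), and power at 0.05 is Φ(d − 1.960).
  - Power 80%: d = 1.645 + 0.842 = 2.487; Φ(0.527) = 0.701; gap 0.800 − 0.701 = 9.9%.
  - Power 90%: d = 1.645 + 1.282 = 2.927; Φ(0.967) = 0.833; gap 0.900 − 0.833 = 6.7%.
- Smallest observed reduction that excludes no effect: 1 − exp(−z × SD × √(2/142)). For an assumed log-scale SD of 0.6 it is 11.1% with a 90% CI and 13.0% with a 95% CI. For SD 1.2 it is 20.9% and 24.4%.

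**2. Forest-plot rows**

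Write the model mean for arm a, visit v and baseline b as τ(a,v) + δ(DKD) + γ(SGLT2i) + β(v)·b.

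- Dose minus placebo at Week 20, in any sub-group, is τ(dose,20) − τ(placebo,20). The δ and γ terms cancel, so every row has the same difference.
- Between two sub-groups, each arm's least-squares mean moves by the same constant. If the plot shows arm means, every arm shifts together.

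Illustration with the SAP's own reference values. Appendix B gives 0.357 for a 30% reduction and 0.223 for 20%; these reproduce as −ln(0.70) = 0.357 and −ln(0.80) = 0.223. Suppose a dose gives 30% in DKD and nothing in non-DKD, with non-DKD share f of 30% to 35% (SAP study design). Taking information share equal to participant share, the additive model shows 1 − exp((1 − f) × ln 0.70) in both rows:

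| f | Reduction shown in both rows |
|---|---|
| 0.30 | 22.1% |
| 0.33 | 21.3% |
| 0.35 | 20.7% |

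Simulated trials of 568 participants (four arms, six visits, 67% DKD, complete data) agree. The additive model averaged 21% in both rows. Separate fits averaged 30% in DKD and 0% in non-DKD. The non-DKD refit in SAP 4.9.2.1 would thus disagree with the non-DKD row of the plot.

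**3. Can the three-stratum refits supply the rows?** No. They split DKD by SGLT2i background and give no pooled DKD row, which a plot by DKD status needs. They also give no pooled row for participants without SGLT2i background.

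**The case against.** The p-values are reported, so the 0.10 test can be read whatever interval is printed. That stands: the test is not compromised, only its display.

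A reader might extend the mismatch to Week 12, where SAP 4.9.3.1 says "The results of the model parameters (estimates, p-values, and 95% CIs) will be presented". The documents do not support this. Alpha 0.10 is stated only for the comparison on dapagliflozin, and no alpha is given for Week 12, which precedes dapagliflozin. Nor is it an inconsistency that SAP 4.9.3.3 says of blood pressure "The 2-sided 90% CI for these differences will be presented" and, for the secondary metrics, "presenting only the 90% CI between each of the AZD5718 doses and placebo". That is a different endpoint with its own stated level.

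On the forest plot, the mention of each sub-group individually could mean the primary specification refitted within each sub-group. That reading is possible, but the source sentence names the primary model and not refits of it, so it must be reworded if refits were meant. The section also specifies least-squares means, not dose-versus-placebo differences. The algebra covers both: differences are identical, and means move by one constant.

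It is also fair that the stratum refits and the homogeneity assessment already address heterogeneity elsewhere, and that the plot is descriptive. This limits the harm, but it does not make a plot with equal rows by construction informative.

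**Conclusion.** Both parts hold, as matters of reporting and display.

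1. At Week 20 the reported interval does not match the stated test. The two disagree in 5% of comparisons under the null and in about 7% to 10% under the planned effect. The second figure assumes 90% to 80% power at two-sided 0.10.
2. Followed literally, SAP 4.9.1.6 gives a sub-group display that cannot show a difference in treatment effect and can contradict the non-DKD refit. This follows from the model and needs no assumption about the data. The figure of about 21% does rest on a deliberately extreme split.

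A reader might infer that a decision turns on a sub-group row passing the 20% reference value. Appendix B applies its reference values to overall placebo-adjusted estimates at the interim, and nothing in the documents rests on a forest-plot row. The primary estimate and its p-value are unaffected.

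**What to change.** **SAP 4.9.2.1.** Present the two-sided 90% CI for each Week 20 dose-versus-placebo contrast, matching alpha 0.10 and the forest plot. Keep the pre-specified 95% CI beside it, labelled descriptive. The 90% interval should not replace the 95% one. A switch to a 16% narrower interval after the unblinded interim review and termination (SAP 4.12 and 4.12.1) could look like a post-interim choice, although the main study team remained blinded. Doing the same at Week 12 is optional.

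**SAP 4.9.1.6.** Take the overall row from the primary MMRM. Take the sub-group rows, one factor at a time, from the MMRM fitted separately within each level. The alternative is to add sub-group-by-visit, treatment-by-sub-group and treatment-by-sub-group-by-visit terms. Plot Week 20 dose-versus-placebo differences with 90% CIs, read descriptively. The Week 20 treatment-by-DKD interaction could also serve as the planned homogeneity assessment; that is a suggestion, not a correction.

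**Cost.** No new data: SAP wording and one extra analysis per factor. The intervals will be wide. SAP 4.14 gives 340 completers of 613 randomised. At 33% non-DKD and four arms, that is 0.33 × 340 / 4 ≈ 28 to 0.33 × 613 / 4 ≈ 50 per arm. A 90% CI around no effect, exp(±1.645 × SD × √(2/n)) − 1, is then:

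| Assumed log-scale SD | n = 28 | n = 50 |
|---|---|---|
| 0.6 | −23% to +30% | −18% to +22% |
| 1.0 | −36% to +55% | −28% to +39% |

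That width reflects what the sub-group data can show; the narrower rows of the additive model would not.
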